7.2.2.6.3 Urinalysis

Urinalysis samples will be collected as described on [Table 7-1](#) and [Table 7-2](#), following local standard practice.

A midstream, second voided morning urine sample will be obtained. Bilirubin, blood, glucose, ketones, leukocytes esterase, nitrite, pH, protein, specific gravity, urobilinogen will be assessed. Microscopic analysis will be performed only in case of positive dipstick.

At the screening visit, a urine sample (at least 15 ml) will be collected for urinary protein/creatinine ratio to assess the eligibility of the patient. First morning void samples must not be used for this analysis.

For patients who develop proteinuria or a worsening of pre-existing proteinuria (assessed by a dipstick) at any visit, please refer to [Section 6.2.1.4](#). Threshold values for proteinuria should be provided.

7.2.2.6.4 Pregnancy and assessments of fertility

All female patients capable of becoming pregnant will have a pregnancy test (serum β -HCG) at the screening visit and visit 15. An urine pregnancy test will be performed as described in [Table 7-1](#) and [Table 7-2](#). The results of the test must be available prior to initiating treatment with any study medication. Positive pregnancy tests will exclude a patient from participating in this trial.

Pregnancy must be recorded on a Clinical Trial Pregnancy Form and reported by the investigator to the local Novartis Clinical Safety & Epidemiology Department. Pregnancy follow-up must be recorded on the same form and must include an assessment of the possible relationship to the Novartis study drug of any pregnancy outcome. Any SAE experienced during pregnancy must be reported on the SAE Report Form.

7.2.2.6.5 Hepatitis Viral tests

Hepatitis viral testing consists of the following items: Hepatitis B surface Antigen (HBsAg), Hepatitis B Surface Antibody (Anti-HBs), Hepatitis C Antibody (Anti-HCV), HCV PCR (Quantitative). Hepatitis viral testing will be conducted at Screening Visit 1 to assess trial eligibility and visit 15.

7.2.2.7 Cardiac assessments

7.2.2.7.1 Electrocardiogram (ECG)

A standard 12 lead ECG will be performed

- at screening visit
- week 48

Interpretation of the tracing must be made by a qualified physician and documented on the ECG eCRF page. Each ECG tracing should be labeled with the study number, patient number, date, and kept in the source documents at the study site. Clinically significant abnormalities present

when the patient signed informed consent should be reported on the Medical History eCRF page. Clinically significant findings must be discussed with Novartis prior to enrolling the patient in the study. New or worsened clinically significant findings occurring after informed consent must be recorded on the Adverse Events eCRF page.

7.2.3 Other assessments

Patient compliance with study treatment will be evaluated using pill count.

Pill count will be measured as per assessments mentioned in [Table 7-1](#) and [Table 7-2](#). The number of tablets of study medication of each strength (125 mg, 250 mg and 500 mg for the DT and 90 mg, 180 mg and 360 mg for the FCT) dispensed will be recorded during the study in the source documents using a subject IMP dispensing log and accountability log and in the Drug Accountability eCRF. Empty bottles and unused medication will be returned by the patient to the study site. Unused study medication tablets will be counted and recorded by the investigator/pharmacist/study staff involved in the study.

7.3 Patient reported outcomes

Please see guidance below on PRO completion:

- In case of treatment switch, the investigator must provide the preference questionnaire to the patient at the immediate next visit and then keep following the schedule of questionnaires pre-planned on [Table 7-1](#) and [Table 7-2](#). Please refer to [Appendix 14.3](#) for further information.
- Completion of PRO questionnaires at screening visit for ICT naïve patient or patients who did not take any ICT treatment within the 6 months prior to screening visit is not required as patient never took any ICT thus they cannot answer to the questionnaire related to palatability, satisfaction and AEs to ICT.
- Completion of palatability questionnaires at screening visit for patients who received Deferoxamine as prior chelation therapy is not required

In case the patient's parents/legal representative and/or the patient are illiterate, the nurse / study coordinator should read each question and the response options to the parent / legal representative. The answer provided verbally by the parent / legal representative can be recorded on the PRO questionnaire by the nurse / study coordinator. In this case, the nurse/study coordinator must not prompt or in any way try to help the parent / legal representative select an answer. This process needs to be carefully document in the source notes.

7.3.1 Preference Questionnaire

The preference questionnaire is a four item questionnaire. There are four separate versions depending on the week(s) that the questionnaire is administered.

For week 48 (primary endpoint) the first item asks the patients (or parents of young patients from 2 to 9 years old) which medicine they are currently taking with the response options: "Tablet to dissolve in liquid", "Film coated tablet ", "Sprinkle powder on food" and "I don't know". The second item asks which of the medicines did the patient "Like best" with the same response options as that of the first item. Finally, the third item asks the patient why he/she preferred the medicine they chose.

For week 28 the first item asks patients to choose from the following medicines: “Tablet to dissolve in liquid”, “Film coated tablet (taken once a day)”, “Tablet (taken 3 times a day)”, “Sprinkle powder on food”, “Injection” and “I don’t know”. The second items remain the same asking which medicine the patients like the best (out of the above response options). Similarly the third item remains the same.

For weeks 4 and 24 the first item asks patients to choose from the following medicines: “Tablet to dissolve in liquid”, “Tablet (taken 3 times a day)”, “Injection” and “I don’t know”. The second items remain the same asking which medicine the patients like the best (out of the above response options). Similarly the third item remains the same.

The following preference attributes are provided:

- Taste
- Aftertaste (taste left in your mouth after you swallow)
- Convenience (it’s not a problem to take your medicine - administration)
- Number of pills
- No/Less side effects
- Can correctly prepare the medicine
- Easier to remember to take the medicine
- Number of times you have to take the medicine
- No/Less pain on the injection site
- Gain my personal time with family and friends
- Other _____

The questionnaire is administered at week 4, week 24, week 28 and week 48. No total score is calculated on the preference questionnaire. Each item will be scored as the proportion of patients who select each response option.

7.3.2 mSICT – patients greater or equal to 10 years old

The Modified SICT (mSICT) questionnaire consists of 15 items that represent 3 domains; Adherence, Preference and Concerns.

The adherence domain consists of 7 items, 6 of which are measured using a 5 point response scale.

Items 4, 5 and 6 use the response format 1 “Never”, 2 “Rarely”, 3 “Sometimes”, 4 “Most of the time”, 5 “Always”; Item 7 uses the response format 1 “Very easy”, 2 “Easy”, 3 “Neither easy nor hard”, 4 “Hard” and 5 “Very hard”; Items 8 and 9 use the response format 1 “Very bothered”, 2 “Quite bothered”, 3 “Moderately bothered”, 4 “A little bothered” and 5 “Not bothered at all”. An Adherence domain score will be calculated by summing these 6 items and as a result a higher score will indicate worse adherence.

Item 10 captures the reasons that the patient did not always take their medication as instructed and is only asked for patients who, at Item 6, indicated that they did not “Always” take their medication as instructed. These patients are instructed to choose all reasons that apply. Each response category will be coded as a binary item, for example taste will be an item with the

response format 0 “Not endorsed”, 1 “Endorsed”. For the “other” option, if there is a common response (>10%) it will be included as an additional binary response category in the analysis, otherwise other will be treated as Other 0 “Not endorsed”, 1 “Endorsed”. This item will be used as a standalone item to better understand the overall Adherence domain.

Satisfaction/preference domain consists of 3 items, 2 assess the patients’ satisfaction with the medication and are measured using a 5 point response scale with the response format: 1 “Very satisfied”, 2 “Satisfied”, 3 “Neither satisfied nor dissatisfied”, 4 “Dissatisfied”, 5 “Very dissatisfied”. A Satisfaction domain score will be calculated by summing these two items. Higher scores will indicate worse satisfaction.

The third item asks the patients to assess which medication for iron overload they prefer; this item will be used as a standalone item in the clinical trial.

Concerns domain consists of 3 items to address any concerns and worries the patient has with their medication. All 3 items are measured on a 5 point response scale with the response format 1 “Always”, 2 “Most of the time”, 3 “Sometimes”, 4 “Rarely” and 5 “Never”. A Concerns domain score will be calculated by summing these 3 items. Higher scores will indicate fewer concerns.

Two additional items (items 14 and 15) will also be scored as standalone items. Item 14 asks patients to choose attributes pertaining to why they chose to prefer a certain medication. Item 15 asks patients to “rank order” the medicines they have taken.

Adherence, satisfaction/preference and concerns domain scores and items will be summarized using standard descriptive statistics (Screening, week 4, week 24, week 28 and week 48).

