7.3.3 Observer Reported mSICT – patients less than 10 years old

Similar to the mSICT for patients greater than 10 years old, an observer reported mSICT will be administered to those patients who are 2-9 years old. Parents or caregivers of these patients will complete the mSICT for behaviors that are observed. The items are similar to the original mSICT however item 15 (the ranking exercise) is not included. In addition, there are 7 items asking the parent to respond from their perspective regarding:

- Feeling worried
- How often medication was given for iron over load
- Thinking to stop giving medication for iron overload
- Following the doctor’s instructions
- Reasons why not always giving medication
- Ease of administrating medication
- Bothered by time it took to administer medication

Adherence, satisfaction/preference and concerns domain scores (which are the same as above) and items will be summarized using standard descriptive statistics (Screening, week 4, week 24, week 28 and week 48).

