For the palatability questionnaire the overall score will be constructed using a scoring matrix from the score of items. Standard descriptive analyses including absolute and relative changes will be performed for both formulations (DT/FCT) for the overall score at Week 4, Week 24, Week 28 and Week 48 and overall score at Screening for iron chelators. The baseline data for treatment period 1 and 2 will be Week 4 and Week 24 data respectively, only one assessment is observed at Screening period.

The standard descriptive analyses include: n, mean, standard deviation, minimum, median and maximum. The 95% confidence interval for the absolute and relative (or difference) change from baseline of the overall score will also be presented for the treatments. In addition to that, summaries will also be performed from the data collected at the time of immediate next visit based on patients who had treatment switching.

Details about scoring and further analyses will be included in the SAP.

mSICT

The Modified SICT (mSICT) questionnaire consists of 15 items that represent 3 domains; Adherence, Preference and Concerns.

For the SICT questionnaire, the score for each domain will be the mean of the score of items included in the corresponding domain. Standard descriptive analyses will be performed for both formulations (DT/FCT) for each domain score at Week 4, Week 24, Week 28 and Week 48 and at Screening for iron chelators. The baseline data for treatment period 1 and 2 will be Week 4 and Week 24 data respectively, only one assessment is observed at Screening period.

The standard descriptive analyses include: n, mean, standard deviation, minimum, median and maximum. The 95% confidence intervals for the absolute and relative (or difference) changes from baseline in all domains will be presented for the treatments. In addition to that, summaries will also be performed from the data collected at the time of immediate next visit based on patients who had treatment switching. .

Details about scoring and further analyses will be included in the SAP.

GI symptoms

The GI symptom consists of 6 items, 5 of which are scored using a 0 – 10 rating scale with item appropriate end anchors to rate the symptom, The sixth item assesses bowel movement frequency during the past 24 hours, using 7 response options.

The GI symptoms will be summarized as analogous to the above questionnaires. Details about scoring and further analyses will be included in the SAP.

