### **mSICT using PRO / ObsRO questionnaire**

The Modified SICT (mSICT) questionnaire consists of 15 items for the PRO version and 22 items for the ObsRO version that represent 3 domains; Adherence, Preference and Concerns.

For the mSICT questionnaire, the score for each domain based on the 15 questions common to both the PRO and ObsRO versions, will be the mean of the score of items included in the corresponding domain. The additional 7 questions that are included in the ObsRO version will be scored as standalone items. Standard descriptive analyses will be performed for both formulations (DT/FCT) for each domain score at Week 4, Week 24, Week 28 and Week 48, and at Screening for iron chelators. The baseline data for treatment period 1 and 2 will be Week 4 and Week 24 data respectively, only one assessment is observed at Screening period. The summary will be provided separately for PRO and ObsRO patient groups.

Weighted mean of both groups will also be reported to highlight the combined result. Separately weighted mean of both the groups for 15 common questions will also be reported. Pooled SD will be provided only if the data from both the groups follow the same distribution.

The standard descriptive analyses include: n, mean, SD, minimum, median and maximum. The 95% CI for the absolute and relative (or difference) changes from baseline in all domains will be presented for the treatments.

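### The mSICT Adherence score adds items that run in opposite directions without reverse-coding, so its stated direction (higher is worse) is false and the SAP does not correct it

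*Protocol*

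**What the plan says.** Protocol 7.3.2 builds the Adherence domain from items 4 to 9, each coded 1 to 5, and states: "An Adherence domain score will be calculated by summing these 6 items and as a result a higher score will indicate worse adherence".

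The response formats are printed in the same section:

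- Items 4, 5 and 6 run from never (1) to always (5).
- The next format is unfavourable at its top code: "Item 7 uses the response format 1 “Very easy”, 2 “Easy”, 3 “Neither easy nor hard”, 4 “Hard” and 5 “Very hard".
- For items 8 and 9 the codes start at very bothered (1) and end with "4 “A little bothered” and 5 “Not bothered at all".

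Item 10 is a follow-up question that "captures the reasons that the patient did not always take their medication as instructed and is only asked for patients who, at Item 6", did not answer always. The protocol keeps item 10 out of the score: "This item will be used as a standalone item to better understand the overall Adherence domain".

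For ages 2 to 9, Protocol 7.3.3 reports "domain scores (which are the same as above) and items will be summarized using standard descriptive statistics".

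Protocol 10.5.6 gives a different rule, "the score for each domain will be the mean of the score of items included in the corresponding domain", and leaves scoring detail to the SAP. SAP 2.11 repeats that each domain score "will be the mean of the score of items included in the corresponding domain". It names no item to reverse and no direction for the score. SAP section 4 records no change to the protocol-specified analyses.

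**The concern.** A sum or mean of items has a direction only if every item points the same way. Here at least one item is unfavourable at its top code and at least three are favourable, so gains on some items cancel or outweigh gains on others. The label attached to the total is then wrong.

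Change in the SICT domain scores is a named secondary endpoint (Protocol Table 3-1, SAP Table 1.2.1). SAP 2.11 plans 95% CIs for absolute and relative change in every domain, a weighted mean combining the patient and observer versions, and domain-score and waterfall plots for the PROs. A programmer who follows the text would produce an Adherence score that, read with the protocol's label, could show a uniform improvement after the move to FCT as no change or as a worsening.

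**Working it through.** The plan gives no figure to reproduce. The check takes each item's direction from its printed anchors and asks whether the worst possible respondent scores above the best, which a higher-is-worse score requires.

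**Item directions (Protocol 7.3.2)**

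| Item | Code 5 means | Favourable at 5? |
|---|---|---|
| 4, 5 | Always (question wording not given) | Unknown |
| 6 | Always takes medicine as instructed, shown by the item 10 skip rule | Yes |
| 7 | Very hard | No |
| 8, 9 | Not bothered at all | Yes |

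**Best and worst totals.** Let k be the number of items 4 and 5 that are favourable at 5 (0, 1 or 2). Then f = 3 + k of the six items are favourable at 5.

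- Best total = 5f + 1(6 - f)
- Worst total = 1f + 5(6 - f)
- Change when all six items improve by one point = f - (6 - f) = 2k

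| k | f | Best | Worst | Change, all six one point better |
|---|---|---|---|---|
| 0 | 3 | 15 + 3 = 18 | 3 + 15 = 18 | 0 |
| 1 | 4 | 20 + 2 = 22 | 4 + 10 = 14 | +2 |
| 2 | 5 | 25 + 1 = 26 | 5 + 5 = 10 | +4 |

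With all items coded so that higher is worse, best = 6, worst = 30 and the change is -6. Items 6 to 9 alone give best 5 + 1 + 5 + 5 = 16 and worst 1 + 5 + 1 + 1 = 8, the reverse of the stated direction.

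**Sum or mean.** Dividing by 6 changes the scale only. For k = 1 the means are 22/6 = 3.67 (best) and 14/6 = 2.33 (worst).

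**Partial improvements.** There are 2^6 - 1 = 63 patterns in which each item either improves by one point or stays the same, with at least one improving. As written, the score behaves as follows:

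| k | Wrong way | No change | Stated way |
|---|---|---|---|
| 2 | 57 | 5 | 1 |
| 1 | 42 | 14 | 7 |
| 0 | 22 | 19 | 22 |

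For items 6 to 9 only (15 patterns) the counts are 11, 3 and 1; the single stated-way pattern is item 7 improving alone. These are counts of patterns, not probabilities of what patients will report. Gains can also be diluted: item 7 two points better and item 8 one point better gives -2 + 1 = -1 instead of -3.

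**Separate side check: palatability, Protocol Table 7-5.** For fixed taste and outcome, compare the score for just enough with the score for not enough or too much. The six differences, in table order, are +1, +1, -1, +1, +1, +1. The exception is bad taste with all swallowed, where just enough scores 4 and the other response scores 5. The documents state no ordering rule, so this is a probable slip inferred from the other five pairs.

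**The case against.** The strongest counter-argument is about reach. This is one domain of one secondary PRO. SAP 2.7.2 plans no formal testing of secondary endpoints, Protocol 7.3.2 also plans item-level summaries, and compliance has its own pill-count endpoint. All of that is true and limits the severity, but item summaries do not make a mislabelled domain score, its CI or its plot correct.

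One could say that reverse-coding is implied. The text presents the direction as a consequence of the summing, and where the protocol wants recoding it writes it out, as for palatability in 7.3.6. That reading does not hold.

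Several narrower points stand:

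- The SAP's fault is an omission: it gives no item direction, no recoding and no score direction. A reported worsening also requires the protocol's label to be carried into the report, and with k = 0 a uniform improvement shows as no change.
- The observer items for ages 2 to 9 are only described as similar, and their response formats are not printed. The fault probably carries over through the shared domain scores but cannot be confirmed item by item.
- The pattern counts do not estimate bias in this trial. The best and worst totals carry the argument.
- Table 7-5 concerns a different instrument, and the documents cannot show which of scores 4 and 5 is right. It is offered only as something to check.

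**Conclusion.** The concern holds, with high confidence for the Adherence direction. The clash between item 7 and items 8 and 9 is plain from their anchors. Adding item 6, whose direction follows from the item 10 skip rule, makes the stated direction fail under every possible wording of items 4 and 5. In the case kindest to the protocol, the score cannot tell the best respondent from the worst.

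This should be fixed before the domain score is reported. The Satisfaction and Concerns scores, pill-count compliance and the Week 48 preference endpoint are not affected. The sum-versus-mean mismatch is minor. The Table 7-5 point is minor and unproven: exchanging scores 4 and 5 would move a score by one point on a 0 to 11 scale, only for respondents who report bad taste and swallowed everything.

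**What to change.** 1. In SAP 2.11 and Protocol 7.3.2, list the direction of each of the six scaled items and code them all one way. To keep higher as worse, apply 6 - x to items 6, 8 and 9. To make higher better, apply 6 - x to item 7. In either case, set items 4 and 5 after reading their wording in the instrument. State the direction of the final score.
2. Choose sum or mean and use it in Protocol 7.3.2, Protocol 10.5.6 and SAP 2.11, over those six items only, with item 10 kept standalone.
3. Check the observer version's response formats and apply the same rule before combining the two versions.
4. Check scores 4 and 5 in Table 7-5 against the instrument's scoring source and exchange them only if the source confirms it.

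The cost is scoring text, a check of the instrument wording and of Table 7-5, and recomputation from responses already collected. The SAP history shows that the Week 48 interim database was locked before the April 2021 versions, so the re-scoring should be recorded as a post-lock change, as was done for the observer GI questionnaire. No new data are needed.

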7.3.3 Observer Reported mSICT – patients less than 10 years old

Similar to the mSICT for patients greater than 10 years old, an observer reported mSICT will be administered to those patients who are 2-9 years old. Parents or caregivers of these patients will complete the mSICT for behaviors that are observed. The items are similar to the original mSICT however item 15 (the ranking exercise) is not included. In addition, there are 7 items asking the parent to respond from their perspective regarding:

- Feeling worried
- How often medication was given for iron over load
- Thinking to stop giving medication for iron overload
- Following the doctor’s instructions
- Reasons why not always giving medication
- Ease of administrating medication
- Bothered by time it took to administer medication

Adherence, satisfaction/preference and concerns domain scores (which are the same as above) and items will be summarized using standard descriptive statistics (Screening, week 4, week 24, week 28 and week 48).

